10.10 Pregnancy Outcome Data

Pregnancy outcome data collected during the study including number of previous pregnancies (and their outcome), any reported problems during pregnancy, estimated due date, pregnancy outcome, delivery type, and infant information will be listed for Safety population.

11 OTHER RELEVANT DATA ANALYSES/SUMMARIES

11.1 Medical History

Medical history will be coded using MedDRA version 22.0 or higher. Medical history will be summarized by SOC and PT by treatment group for the Safety population and listed for the Safety population. Summaries of SOC and PT will be sorted alphabetically by SOC and by descending frequency of PT in the BCG group. If a participant has more than one medical history even at a given level (e.g., SOC and PT), the participant will only be counted once within that level. A listing of medical history will also be presented.

Number and percentage of participants reporting an acute respiratory or febrile illness or lost sense of smell (ie, COVID-like symptoms) in the past 6 Months will be summarized by treatment group and listed for the Safety population.

No imputation of partial or missing dates will be performed for medical history and study days will not be presented for these cases.

11.2 Concomitant Medications

Concomitant medications will be coded using the World Health Organization (WHO) Drug Global Mar2019 or later version. A concomitant medication is defined as a medication with a stop date on or after the first dose date, thus a medication that is ongoing at the time of a participant's vaccination is considered concomitant. Partial and missing dates for concomitant medications will be imputed using the guidance in Appendix 5. The recorded partial/missing dates will be displayed in the listings and study days will not be presented for these cases.

Medications will be summarized by Anatomical Therapeutic Chemical (ATC) level 3 and preferred name by treatment group for the Safety population. Summaries of ATC level 3 and preferred name will be sorted alphabetically by ATC level 3 and by decreasing frequency of preferred name in the BCG group. If a participant has more than one medication at a given level (e.g., ATC level 3 and preferred name), the participant will only be counted once at that level.

Medications will be listed for the Safety population.

For participants in the mITT for efficacy population who have sustained conversion events, if preventive treatment can be identified in the database, the number of participants who had preventive treatment initiated following the sustained conversion event will be tabulated by site and overall and a corresponding by participant listing will be generated. The list of concomitant medications associated with preventive treatment will be provided by clinical team and will be included as source for planned analyses.

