5.2. Exclusion Criteria

Participants are excluded from the study if any of the following criteria apply:

Medical Conditions and History:

- 8. Acute illness on Study Day 1 (refer to Section 5.4 for additional details). NOTE: This is a temporary exclusion for which the subject may be re-evaluated.
- 9. Body temperature ≥37.5°C on Study Day 1 (refer to Section 5.4 for additional details). NOTE: This is a temporary exclusion for which the subject may be re-evaluated.
- 10. History or evidence of any clinically significant disease, including severe eczema and severe asthma, or any acute or chronic illness that might affect the safety, immunogenicity, or efficacy of study vaccine in the opinion of the investigator
- 11. Any current medical, psychiatric, occupational, or substance abuse problems that, in the opinion of the investigator, will make it unlikely that the participant will comply with the protocol

- 12. History of autoimmune disease
- 13. History or evidence of active TB disease
- 14. History or laboratory evidence of any past or present possible immunodeficiency state including, but not limited to, any laboratory indication of HIV-1 infection
- 15. History of allergic disease that is likely to be exacerbated by any component of the study vaccine

Prior/Concomitant Therapy

- 16. History of treatment for active TB disease or history of latent Mtb infection
- 17. Received a TST within 6 months prior to Study Day 1
- 18. Received immunosuppressive treatment, e.g., chemotherapy, biologics or radiation therapy, or used immunosuppressive medication (daily steroid equivalent of ≥5mg prednisone) within 42 days before Study Day 1. Inhaled and topical corticosteroids are permitted.
- 19. Received immunoglobulin or blood products within 42 days before Study Day 1
- 20. Planned administration/administration of a licensed vaccine in the period starting 28 days before and ending 28 days after Study Day 1

Prior/Concurrent Clinical Study Experience

- 21. Received investigational TB vaccine at any time prior to Study Day 1
- 22. Received any investigational drug therapy or investigational vaccine within 180 days before Study Day 1, or planned participation in any other clinical trial using investigational product during the study period

Diagnostic assessments

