Appendix 4 Study Visit Intervals

NA = not applicable PC = post-conversion.

Note that after Day 71, timepoints and intervals will be measured in calendar months.

Refer to Section 7.4 of the protocol for intervals based on COVID-19 contingency plans.

Imputation Rules for Partial Dates (D=day, M=month, Y=year)					
Parameter	Missing	Additional Conditions	Imputation		
Start Date	D only	M and Y same as M and Y of date of vaccination	Date of vaccination		
		M and/or Y not the same as date of vaccination	First day of month		
	M and D	Y same as Y of date of vaccination	Date of vaccination		
		Y not the same as date of vaccination	Jan 01 of Y		
	M, D, and Y	Non-date completely missing	Day prior to date of vaccination		
Stop Date	D only	M and Y same as M and Y of date of discontinuation/completion of study M and/or Y not the same as date of discontinuation/completion of study	Date of discontinuation/ completion of study Last day of month		
	M and D	Y same as Y of date of discontinuation/completion of study Y not the same as date of discontinuation/completion of study	Date of discontinuation/ completion of study Dec 31 of Y		
	M, D, and Y	None – date completely missing and NOT ongoing	Date of discontinuation/ completion of study		

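### For preventive-therapy records with an incomplete start date, the SAP's imputation rules can place the start before sustained conversion and drop the participant from the planned uptake count

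*SAP*

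**What the plan says.** SAP 11.2 (Concomitant Medications) contains both a general rule and a specific count.

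- The general rule: "Partial and missing dates for concomitant medications will be imputed using the guidance in Appendix 5".
- The count, planned for mITT participants with sustained conversion: "the number of participants who had preventive treatment initiated following the sustained conversion event will be tabulated by site and overall". It is made only if the data allow such treatment to be recognised, and a by-participant listing accompanies it.
- The source of the count is the concomitant-medication data: "The list of concomitant medications associated with preventive treatment will be provided by clinical team".

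The Appendix 5 table gives these start-date rules:

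- Day, month and year all missing: "Day prior to date of vaccination".
- Only the year recorded: the vaccination date where the condition is "Y same as Y of date of vaccination", otherwise 1 January of the recorded year.
- Only the day missing: the vaccination date if the month and year match those of vaccination, otherwise "First day of month".

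SAP Appendix 6 dates the sustained conversion event at the initial conversion. SAP 9.1 requires that conversion to follow a negative QFT at Day 71 or, if Day 71 was missed, at the first in-person visit after it. Protocol 8.3.6 provides for preventive therapy, by referral or at the site, once conversion is sustained.

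**The concern.** The Appendix 5 start-date rules pull an incomplete date back towards vaccination or to the beginning of the recorded period. The uptake count asks whether treatment started after an event that may come months or years after vaccination. For that question, pulling the start back can reverse the true order and remove a treated participant from the table.

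The imputed value is also implausible for these records. Participants are QFT negative at screening, and Protocol 5.2 excludes "History of treatment for active TB disease or history of latent Mtb infection". The day before vaccination is therefore about the least credible start for preventive therapy.

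Incomplete starts are foreseeable, although their frequency is unknown. Protocol 6.5 asks for start and end dates of medications taken through Day 71, and its sentence on TB medication through the last visit does not repeat that request. Therapy given by outside referral would reach the database second-hand.

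At stake is the SAP's only planned summary of whether sustained converters started the therapy described in Protocol 8.3.6. The table is split by site. If referral sites hold more incomplete dates, the undercount would differ between sites and could look like a difference in care.

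**Working it through.** The plan states no figure for this point, so there is none to reproduce. The check applies the Appendix 5 start-date rules and compares the imputed start with the event date.

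**Inputs from the documents.** The start-date rules are in Appendix 5, the event date (initial conversion) is in Appendix 6, and the requirement for a prior negative QFT is in SAP 9.1.

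**Assumptions.** The 6-month confirmation comes 182 days after initial conversion. Therapy starts 0 to 180 days after confirmation. Initial conversions are spread evenly over the calendar, in years after the vaccination year.

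**Wholly missing start.** The imputed start is the vaccination date minus 1 day. Every event falls after the Day 71 (or later) negative test, so the imputed start precedes the event in 100% of such records.

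**Year-only start, therapy in a later year than vaccination.** The imputed start is 1 January of the therapy year. It precedes the event only if the initial conversion is in that same year. With L days from initial conversion to therapy start, the share misplaced is about (365 − L)/365.

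| Therapy start after confirmation | L (days) | (365 − L)/365 | Day-by-day count |
|---|---|---|---|
| 0 days | 182 | 183/365 = 50% | 49.9% |
| 30 days | 212 | 153/365 = 42% | 41.6% |
| 90 days | 272 | 93/365 = 25% | 25.2% |
| 180 days | 362 | 3/365 = 1% | 0.6% |

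**Year-only start, therapy in the vaccination year.** The imputed start is the vaccination date, which also precedes the event. On the scheduled visits this will rarely arise for therapy given after confirmation: the first test after Day 71 is at Month 6, and confirmation then comes at about Month 12 (6 + 6).

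**Only the day missing.** The imputed start is the first of the therapy month. With therapy at least 182 days after initial conversion, the event is always in an earlier month, so 0% are misplaced.

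**Illustration (dates assumed).** A participant is vaccinated on 15 September 2020, converts at Month 18 (15 March 2022) and starts therapy in October 2022.

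- With no start date, the record is dated 14 September 2020 and the participant is not counted.
- With only 2022 recorded, it is dated 1 January 2022, before the conversion, and the participant is not counted.
- Had the conversion been at Month 24 (15 September 2022) with therapy in 2023, a year-only record would be dated 1 January 2023 and the participant would be counted.

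**The case against.** The strongest reply is that the SAP never says the imputed dates drive this count. That follows only from the general sentence in 11.2. The table is descriptive, conditional on preventive treatment being identifiable, and not split by arm. A reader could also spot the problem, because "The recorded partial/missing dates will be displayed in the listings and study days will not be presented for these cases". SAP 7.5 even states that missing data will not be imputed.

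Part of this stands. The harm is small and partly visible. But a listing does not correct a table, and 11.2 is the specific rule for these dates, so it prevails over the general statement in 7.5. SAP 11.1 exempts medical history from date imputation, so an exemption could have been written here too. Read literally, 11.2 gives a wrong answer for a record with no start date.

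A reader might infer more than the documents support:

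- *That preventive therapy in general is misdated.* Only records with incomplete start dates are touched.
- *That every year-only start is lost.* At least about half would still be counted under the assumptions above.
- *That about 92% of year-only starts are lost.* That figure holds for therapy 30 days after confirmation if timing is measured from confirmation. The only event date the SAP defines is initial conversion, where the figure is 42%.
- *That some 5 to 35 participants are miscounted.* This takes 118 × 10% × 42% = 5 and 118 × 30% × 100% = 35. The 10% and 30% are assumed, and 118 is the minimum number of events that triggers the analysis, not a number treated.
- *That TB drugs would be reported as used before vaccination.* SAP 11.2 defines concomitant use by stop date, plans no prior-medication table, and lists dates as recorded.
- *That the QFT endpoints or TB incidence are distorted.* SAP 4.3.3, 9.4 and 10.9 do not use the timing of preventive therapy.

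**Conclusion.** The point holds for incomplete start dates only. A wholly missing start is always placed before the event, and this needs no assumption beyond applying 11.2 as written. A year-only start is misplaced when the initial conversion falls in the same calendar year as the therapy: about 50% of such records if therapy begins at confirmation, falling to about 1% if it begins 180 days later. Those shares rest on a 182-day confirmation and even calendar spread. A start missing only its day is not misplaced when timing is measured from initial conversion and therapy follows confirmation.

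The number of participants lost cannot be computed, because neither document gives the frequency of incomplete dates. The consequence is a possible undercount in one descriptive table. The primary and secondary efficacy tests do not use it. This is a minor point, worth correcting because the correction is cheap.

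**What to change.** Amend SAP 11.2, for this count only:

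1. Exempt TB preventive therapy from the Appendix 5 start-date imputation.
2. State the reference date for treatment that follows the event: initial conversion or the 6-month confirmation.
3. Place an incomplete start using any recorded year or month together with the visit interval in which the therapy was first reported. The schedule of activities asks about TB medication at every scheduled visit from Day 1. If the possible interval lies wholly on one side of the reference date, classify the participant accordingly.
4. Tabulate participants whose timing is still unknown in a separate row, initiated, date unknown, by site and overall, instead of leaving them out.

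The cost is a few sentences and a small derivation change. No new data are needed, and Appendix 5 can stay as it is for other medications.

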13 APPENDICES

Appendix 1 Schedule of Assessments

Study Visit Day (D) or	Screen	D1	D8 ^a	D29 ^b	D71 ^{b,c}	M6,12,18,	Suspected	Discon	Notes
Month (M)	D -28 to					24,30, 36,	TB Visit	Visit ^d	
	D -1					42, 48			
	V	~							Confirm eligibility prior to
Eligibility criteria verification	X	×							randomization on D1
Obtain informed concept & accept	V								Re-consent of participants enrolled
Obtain mormed consent & assent	^								before study pause
Medical history	Х								
Physical examination	х								
Focused physical examination		х	х	х	х	х			Exam if indicated by interval history
Body weight and height									
measurement	x	x				X			
Body temperature	х	Х							
Interval history		Х	х	Х	Х	Х			
Vital signs	Х	х							
Distribute/review diary cards		Х							
Collect diary cards			Х						
Distribute memory aid			Х						
Collect memory aid				Х					
Solicited AEs		Х	х						
									AEs will be collected from the time
Unsolicited AEs	x	Х	Х	х					informed consent is obtained.
All serious adverse events (SAEs) and	I,					X			
AESI	x	X	Х	X	X	(M6 only)			
Serious ADRs		Х	Х	Х	х	Х		Х	Collected through the last study visit

Study Visit Day (D) or Month (M)	Screen D -28 to	D1	D8ª	D29 ^b	D71 ^{b,c}	M6,12,18, 24,30, 36,	Suspected TB Visit	Discon Visit ^d	Notes
Concomitant prescription medications & antipyretic/anti- inflammatory drugs	0-1	x	x	x	×	42,40			
Immunosuppressive and/or TB medication (curative & preventive)		х	х	х	х	x		х	
Ask about pregnancy		Х	Х	Х	х	Х		х	
Injection site examination			Х	х	Х	X (M6 only)			
TB symptom screen	Х			Х	х	Х		х	
βHCG test all females (mL)	5	x							Serum test at screening Urine test on Day 1, and if pregnancy suspected on subsequent visits
BCG or placebo administration		Х							
Urinalysis	x								May be repeated as described in Protocol Section 8.
QFT assay (mL)	4				4	4			^e regarding unevaluable sample
HIV test (mL) with pre- and post-test counselling	3					3	3		At screening, and M12, 24, 36, 48 only, and if TB disease is suspected. ^f regarding unevaluable screening sample
Serum chemistry (mL)	5								Refer to Protocol Section 8.2.5
CBC, differential (mL)	2.5								f regarding unevaluable screening sample.
Absolute blood cell count (mL)		0.5	0.5	0.5	0.5	0.5			
PAXgene tube for RNA (mL)		2.5	2.5	2.5	2.5	2.5			

Study Visit Day (D) or Month (M)	Screen D -28 to D -1	D1	D8ª	D29 ^b	D71 ^{b,c}	M6,12,18, 24,30, 36, 42, 48	Suspected TB Visit	Discon Visit ^d	Notes
Subset only : Whole blood for ICS (mL) for CD4 and CD8 T cells		6		6	6	6 (M6 only)			First 80 10- to 12-year-old participants enrolled at SATVI
PBMC and plasma for CoP & CoR (mL)		34			34	26			
Serum for CoP & CoR (mL) (innate and adaptive)		10	10	10	10	10			
Sputum samples or other appropriate samples for smear microscopy, mycobacterial culture, and GeneXpert							x		
Nasal or oropharyngeal sampling for SARS-CoV-2 diagnostic test	х	х	х	x	x	х			Samples collected only if participant presents with suspected COVID-19
SARS-CoV-2 serology (mL)	5					5 at M6, M12, M18 and M24			If enrolled before study pause: collect at the next feasible biannual visit (e.g., M6, M12, etc) and biannually thereafter for 24 months
Per visit approximate phlebotomy volume (vol.) (mL) (includes ICS subset)	19.5	53	13	19	57.0	52 at M6 46 at M12			Vol. at M18, 24, 30, 36, 42, 48 = 46 mL per timepoint, excluding SARS
Cumulative approximate vol. (mL) includes ICS subset	19.5	72.5	85.5	104.5	161.5	259.5 Year (Yr)1 ^g			Yr 2=351.5mL Yr 3 =443.5mL Yr 4=535.5mL excluding SARS
Cumulative approximate vol. (mL) excludes ICS subset	19.5	66.5	79.5	92.5	143.5	235.5 Yr 1 ^h			Yr 2 =327.5mL Yr 3=419.5mL Yr 4 =511.5mL excluding SARS
Cumulative approximate vol. (mL)	24.5	77.5	90.5	109.5	166.5	269.5			Yr 2=371.5 mL

Study Visit Day (D) or	Screen	D1	D8ª	D29 ^b	D71 ^{b,c}	M6,12,18,	Suspected	Discon	Notes
Month (M)	D -28 to					24,30, 36,	TB Visit	Visit ^d	
	D -1					42, 48			
after study pause (including SARS-						Yr 1 ^g			Yr 3 =463.5mL
CoV-2 serology) includes ICS subset									Yr 4=555.5mL

X indicates procedure to be performed and number indicates blood volume collected (volumes listed are approximate).

^a Laboratory testing for innate host responses

^b Laboratory testing for adaptive host responses

^c QFT test to determine who to exclude from mITT efficacy analysis (end of wash-out period)

^d A discontinuation (discon) visit will be scheduled for participants who discontinue or withdraw, whenever possible.

^e QFT sampling: If the blood sample collected for QFT cannot be evaluated (e.g., insufficient volume; damage, hemolytic or lost sample, etc.), collection of a second (repeat) blood sample is permitted to enable evaluation of the primary efficacy endpoint. If the QFT sample was successfully run and has a reported result, including "indeterminate", collection of a second (repeat) blood sample is not permitted.

^f If a blood sample collected for screening cannot be evaluated (e.g., insufficient volume; damaged, hemolytic, or lost sample, etc.) a second (repeat) blood collection is permitted to enable evaluation of study eligibility. The repeat blood collection must occur within the protocol-defined screening visit window. If a screening blood sample was successfully run and has a reported result to determine eligibility, a second (repeat)

blood collection is not permitted.

^g Including subset and includes PC visits Table 3: maximum vol. of whole blood collected through M48 = 637.5mL

^h Participants not in subset, includes PC visits Table 3: maximum approximate vol. of whole blood collected through M48= 613.5mL

Appendix 4 Study Visit Intervals

NA = not applicable PC = post-conversion.

Note that after Day 71, timepoints and intervals will be measured in calendar months.

Refer to Section 7.4 of the protocol for intervals based on COVID-19 contingency plans.

Imputation Rules for Partial Dates (D=day, M=month, Y=year)					
Parameter	Missing	Additional Conditions	Imputation		
Start Date	D only	M and Y same as M and Y of date of vaccination	Date of vaccination		
		M and/or Y not the same as date of vaccination	First day of month		
	M and D	Y same as Y of date of vaccination	Date of vaccination		
		Y not the same as date of vaccination	Jan 01 of Y		
	M, D, and Y	Non-date completely missing	Day prior to date of vaccination		
Stop Date	D only	M and Y same as M and Y of date of discontinuation/completion of study M and/or Y not the same as date of discontinuation/completion of study	Date of discontinuation/ completion of study Last day of month		
	M and D	Y same as Y of date of discontinuation/completion of study Y not the same as date of discontinuation/completion of study	Date of discontinuation/ completion of study Dec 31 of Y		
	M, D, and Y	None – date completely missing and NOT ongoing	Date of discontinuation/ completion of study		

Appendix 5 Prior and Concomitant Medications Date Imputation

Appendix 6 Time to Event Derivation Details

Initial QFT Conversion/ Month 3 post initial conversion/Month 6 post initial conversion ¹	Event/ Censored	Date of Event/Censoring
Sustained conversion prior to date of data cut-off (i.e. Positive/Positive/Positive: -/-/-//+/+/+/any/any)	Event	Date of Initial Conversion to QFT positive
No initial conversion prior to date of data cut-off (-/- /-//-/-)	Censored	Minimum (date of last non-missing QFT result, date of data cut-off)
Initial converters with a 3-month positive QFT and missing 6-month results prior to date of data cut-off (i.e. Positive/ Positive/missing: -/-/-//+/+/- /+/+/Missing)	Censored	Date of initial conversion to QFT positive
Initial converters with a 3-month negative QFT and missing 6-month result prior to date of data cut-off (i.e. Positive/ Negative/Missing: -/-/-//+/-/Missing)	Censored	Date of initial conversion to QFT positive
Initial converters with a missing 3-month and positive 6-month result prior to date of data cut-off (i.e., Positive/Missing/Positive: -/-//+/Missing/+)	Censored	Date of initial conversion to QFT positive
Initial converters with a missing 3-month and negative 6-month results prior to date of data cut-off (i.e. Positive/Missing/Negative: -/-/-//+/Missing/-)	Censored	Date of initial conversion to QFT positive
Initial converters with missing 3-month and missing 6-month results prior to date of data cut-off (i.e., Positive/Missing/Missing: -/-/- //+/Missing/Missing)	Censored	Date of initial conversion to QFT positive

¹indeterminate QFT results are counted a negative test result.

